		from Sample Size Determination (Section 9.1), because already described elsewhere (Sections 3.1, 3.2 and Section 3.5, respectively). 16) Included other areas of expertise that may be incorporated into the E-DMC (Section 9.6). 17) Administrative changes to improve consistency and clarity throughout document (eg, updated appendix of abbreviations to include new terms; replaced previously defined terms with abbreviations or acronyms where appropriate; corrected error for hybrid, not human, creatine kinase [hCK] [Section 1.1]: corrected error to reflect Zarit Burden Interview vs. Zarit Burdent Inventory [Section 7.1.1.1 and Abbreviations]; added clarity for consistency that daily glucocorticoid regimen is required and compliance should be captured through at least 1 year after receipt of PF-06939926 [Schedule of Activities, Sections 1.5.1, 5]; added clarity around permitted medications to treat or prevent adverse events [Section 5.7.1]; adjusted placement of clarification for repeat Screening labs [Section 6.1]); added clarification that concomitant medications or therapies may also be considered when assessing the causality of a serious adverse event.
Amendment 6	03 March 2021	1) Added the following Exclusion Criteria:
		• For clarification: Prior treatment with gene therapy, defined as any therapy introducing exogenous DNA or intended to permanently alter the endogenous DNA. Gene therapy (other than study drug) will be prohibited for the duration of the study.
		For clarification: Exposure within 6 months prior to Screening (Visit 1) to any treatment designed to increase

dystrophin expression (including, but not limited to exon-skipping agents and nonsense read-through). These treatments will also be prohibited during the period between Screening (Visit 1) and Day 1 (Visit 3) and for the first year of the study.
• To prevent hypersensitivity reactions: Known hypersensitivity to any of the components of the study drug or solution for infusion, such as hypersensitivity to albumin or a diagnosis of (or symptoms suggestive of) hereditary fructose intolerance (HFI). Symptoms suggestive of HFI include nausea, vomiting, bloating, stomach cramps, or diarrhea following the ingestion of sweet foods or drinks, or a pattern of avoiding sweet foods or drinks.
 To account for elevated values as a result of treatment with steroids that do not reflect renal impairment: Changed Cystatin C criterion from > 1.0 mg/L to >1.2 × ULN
• Platelets $<150 \times 10^3/\mu L$;
2) For clarification, added the length of time that the study drug is stable. (Section 5.4)
3) Schedule of Activites - Added that the baseline NAb to AAV: will be collected and sent to the central laboratory, but will only be analyzed and reviewed prior to Day 1 (Visit 3), if the study team determines that Day 1 (Visit 3) will be more than 55 days after the Screening visit (Visit 1).
4) Clarified the use of cardiovascular medications and changed may to must for the receipt of the Meningococcal Vaccine.

		 (Section 5.7.1) so that there is consistency with among all protocols for this program. 5) Added Cardiac Troponin to Triggers for Additional Safety Monitoring (Section 7.2.12). 6) Clarified when the primary safety analysis will be conducted (Section 9.5). 7) To allow for the sites to have flexibility, added that trained respiratory therapists can perform PFTs (Section 7.5). 8) Added an appendix to include alternative measures during public emergencies (Appendix 1). 9) Added additional abbreviations to Appendix 2.
Amendment 7	03 June 2021	1) Section 1.5.3 Other Risks: Added the possible risks of the use of a PICC line for blood draws since a PICC line may be used. 2) Section 1.4 Study Design Rationale, Section 3.1 Study Overview, Section 3.2 Planned Number of Subjects, and Section 9.1 Sample Size Determination: changed the sample size to 35. 3) Section 3.5 Dose Progression and Stopping Rules: Changed GLDH >2.5 × ULN to "Any set of laboratory results meeting Hy's Law" for the criteria to halt further enrollment, and clarified that the E-DMC will review data for the subjects with the clinical events that prompted the review instead of all available data. The E-DMC has reviewed 3 cases of elevated GLDH levels and agreed that the review of subsequent cases was not necessary unless Hy's Law was met.

		4) Section 5 Study Treatments: Adjusted the glucocorticoid regimen post-infusion with PF-06939926 to allow for a slower tapering and to minimize the risk of adrenal insufficiency.
		5) Section 5.7.2 Prohibited Therapies: Added that subjects will be able to receive an mRNA, or DNA-based, or non-replicating viral vector vaccine (eg, against SARS-CoV2) within specified time windows.
		6) Added a requirement that subjects who experience an event compatible with aHUS will be screened for a genetic predisposition to aHUS to obtain information that may contribute to an understanding of the risk for developing aHUS.
		7) Section 7.2.1 Clinical Laboratory: Clarified that the PICC line can only be used for blood draws and not study drug administration.
		8) Table 1 Central Laboratory Tests: Added magnesium to the chemistry panel.
		9) A cohort was added as an appendix to evaluate the use of sirolimus to mitigate the risk of complement-mediated events related to PF-06939926.
		10) Changed "first" cohort to "low-dose" cohort and "second" cohort to "high-dose" cohort throughout the document.
Amendment 8	02 September 2021	1) Schedule of Activities Footnote I and Section 6.1: Changed "may' to "will" be collected and tested for the ADA to minidystrophin at screening and added ADA to minidystrophin at Week 2/Day 14 to the SoA and Section 6.4. This change is to identify subjects with a potentially higher risk of immune reactions.
		2) Schedule of Activities Footnote L: added that DMD genetic testing will only be

- obtained and sent to the central lab if required to confirm the diagnosis of DMD.
- 3) Section 4.2 Exclusion criteria: Addition of exclusion criterion to exclude subjects with specific mutations in the dystrophin gene considered to increase the risk of immunemediated adverse reactions. This was a recommendation by the E-DMC based on the review of the immune and genetic data from studies C3391001 and C3391003.
- 4) Appendix 1: Sirolimus Cohort Schedule of Activities: Remote Visit 2.4 Phone Contact, the range of the visit window was changed from "+2 days" to "+3 days" to accommodate for the length of time it could take to receive the sirolimus trough concentration level back from the lab. Also removed the footnote that referenced the Platelet and C4 levels and changed "additional clinical safety labs" to "Platelets and C4 Levels" within the table. 5) Appendix 1: Sirolimus Cohort Schedule of Activities: Remote Visit 3.1 Phone Contact, a phone contact was added for possible sirolimus dose level adjustment on Day 6 (+3 days) along with Footnote b "Sirolimus dose adjustments as soon as the trough concentration level from Day 4 is available." This information was included on the sirolimus dosing table within Appendix 1 but was inadvertently originally omitted from the sirolimus cohort Schedule of Activities.
- 6) Appendix 1: Sirolimus Cohort Schedule of Activities: "Sirolimus trough level" replaced with "Sirolimus trough level (locally)" This information was included on the sirolimus dosing table within Appendix 1 but was inadvertently originally omitted from the sirolimus cohort Schedule of Activities.
- 7) Appendix 1: Sirolimus Cohort Schedule of Activities: For remote visits 4.2 and 5.2, the following sentence was added as footnote C: "Unless clinical concern and/or subject

preference warrants an in-person visit, remote visits may be performed." This sentence was added to allow for flexibility so an in person visit is allowable.
8) Appendix 1: Sirolimus Cohort: Cohort Intervention: Added guidance on how to calculate the BSA for the sirolimus dose when required based on the subject's weight.
9) Added Appendix 3: Protocol Amendment History
10) Appendix 4 Abbreviations: Added additional abbreviations.

Appendix 4. Abbreviations

This following is a list of abbreviations that may be used in the protocol.

Abbreviation	Term
%pFVC	percent predicted forced vital capacity
4SC	Four Stair Climb
6MWD	six minute walk distance
6MWT	Six Minute Walk Test
AAV	adeno-associated virus
AAV9	adeno-associated virus, serotype 9
ACE	angiotensin converting enzyme
ADA	anti-drug antibodies
ADLs	activities of daily living
AE	adverse event
aHUS	atypical hemolytic uremic syndrome
ALT	alanine aminotransferase
ALP	alkaline phosphatase
ANA	Antinuclear antibody
ANC	absolute neutrophil count
aPTT	activated partial thromboplastin time
AST	aspartate aminotransferase
ATS	American Thoracic Society
BBS	Biospecimen Banking System
BMD	Becker muscular dystrophy
BP	blood pressure
BSA	Body surface area
C4	Complement 4
C5b-9	Complement 5b-9
CDC	Center for Disease Control
cDNA	complementary DNA
CE	clinical evaluator
CINRG	Cooperative International Neuromuscular Research Group
CIOMS	Council for International Organizations of Medical Sciences
CK	creatine kinase
CK-MB	creatine kinase myocardial b fraction
CMV	Cytomegalovirus
CNS	central nervous system
COVID-19	Coronavirus disease 19
CR	cysteine-rich
CRF	case report form
CRP	C-reactive protein
CSA	clinical study agreement
C-SSRS	Columbia Suicide Severity Rating Scale
CT	c-terminal
cTnI	cardiac troponin I

Abbreviation	Term	
CYP3A4	Cytochrome P450 3A4	
DAP	Dystrophin-associated protein	
DILI	drug-induced liver injury	
DGC	Dystrophin-associated glycoprotein complex	
DMD	Duchenne muscular dystrophy	
DNA	deoxyribonucleic acid	
EC	ethics committee	
ECG	Electrocardiogram	
E-DMC	external data monitoring committee	
E-DMC EDP	e e	
EDTA	exposure during pregnancy	
	edetic acid (ethylenediaminetetraacetic acid)	
ELISpot	enzyme-linked immunospot	
ELISA	enzyme-linked immunosorbent assay	
FOLLAG		
EQ VAS	EuorQol visual analogue scale	
ERS	European Respiratory Study	
ESR	erythrocyte sedimentation rate	
ET	Early Termination	
EU	European Union	
EudraCT	European Clinical Trials Database	
FDA	Food and Drug Administration	
FEV	forced expiratory volume	
FIH	first-in-human	
FIP	first-in-patient	
FVC	forced vital capacity	
GCP	Good Clinical Practice	
GGT	gamma-glutamyl transferase	
GLDH	glutamate dehydrogenase	
GMP	good manufacturing practice	
HAV	hepatitis A virus	
HBsAG	hepatitis B surface antigen	
hCK	hybrid creatine kinase	
HCVAb	hepatitis C antibody	
HFI	hereditary fructose intolerance	
HR	heart rate	
HT	height	
IA	interim analysis	
IB	Investigator's Brochure	
ICD	informed consent document	
ICH	International Conference on Harmonisation	
ID	Identification	
IFA	Immunofluorescence assay	

Abbreviation	Term
IHC	Immunohistochemistry
IM	Intramuscular
INFα	interferon alpha
INFβ	interferon beta
IgG	immunoglobulin G
IgM	immunoglobulin M
IND	investigational new drug application
INR	international normalized ratio
IP-10	Interferon gamma-induced protein 10
IRB	institutional review board
IRT	interactive response technology
ITAC	Interferon-inducible T-cell alpha chemoattractant
ITR	inverted terminal repeats
IV	Intravenous
K ₂ EDTA	dipotassium ethylenediaminetetraacetic acid
Kda	kilo-dalton
Kg	Kilogram
LC-MS	liquid chromatography/mass spectrometry
LFT	liver function test
LSLV	last subject last visit
LVEF	left ventricular ejection fraction
MenACWY	meningococcal conjugate
MenB	serogroup B meningococcal
MHP	mental health provider
MRI	magnetic resonance imaging
mRNA	messenger ribonucleic acid
MSW	Master's level Clinical Social Workers
N	Number
N/A	not applicable
NAb	neutralizing antibodies
NOAEL	no observed adverse effect level
NSAA	North Star Ambulatory Assessment
qPCR	quantitative polymerase chain reaction
QTcF	Fridericia's correction formula
PACL	protocol administrative change letter
PCD	primary completion date
PD	pharmacodynamics
PEFR	peak expiratory flow rate
PFT	pulmonary function test
P-gp	P-glycoprotein
PI	principal investigator
PICC	peripherally inserted central catheter
PK	pharmacokinetic(s)
PNP	psychiatric nurse practitioners

Abbreviation	Term	
CCI		
P-selectin: protein-selectin	P(platelet)-selectin glycoprotein ligand-1	
PT	prothrombin time	
PUL	Performance of Upper Limb	
rAAV	Recombinant AAV	
RBC	red blood cell	
RNA	ribonucleic acid	
ROA	route of administration	
SAE	serious adverse event	
SAP	statistical analysis plan	
SARS-CoV-2	severe acute respiratory syndrome coronavirus 2	
SD	Standard deviation	
SMA	Spinal muscular atrophy	
SoA	schedule of activities	
SOC	system organ class	
SOP	standard operating procedure	
SRSD	single reference safety document	
SSID	single subject's identification	
TBili	total bilirubin	
TEAEs	treatment emergent AEs	
temp	temperature	
TG	Transgene	
ULN	upper limit of normal	
UL-PROM	Upper Limb Patient Reported Outcome Measure	
US	United States	
USPI	United States Package Insert	
Vg	vector genomes	
WB	Western blot	
Wt	weight	
CCI		

Document Approval Record

Document Name: C3391001 Protocol Amendment 9 (Clean) 07 March 2022

Document Title: A PHASE 1B MULTICENTER, OPEN-LABEL, SINGLE ASCENDING

1. VERSION HISTORY

Table 1.Summary of Changes

Version/ Date	Associated Protocol Amendment	Rationale	Specific Changes
6 27-Oct-2022	Amendment 9 7-Mar-2022	Analysis of study endpoints utilizing external controls will be described separately in a supplementary SAP. SAP content clarification. Updated the analysis description related to the sirolimus cohort given the sample size.	Throughout the SAP: Removed content related to synthetic controls (or external controls) including Section 4. Section 5.1, Section 5.3.5, Section 5.4, Section 6.3.2.1, Section 6.3.4.1, Appendix 2 and methods of deriving the external control sections, related reference articles. Section 2.1, 2.2, 2.4.1: Consolidated description of study objectives, endpoints, and estimands into a single table. Removed estimand for safety, immune response, viral vector shedding, and the sirolimus evaluation endpoints. Sections 2.1, 3.2.1.2, and 6.2.2: Added endpoints and analyses for the newly developed immunofluorescence assay mini-dystrophin specific antibody. Sections 2.1, 3.2.1.1, and 6.2.1: Removed Western Blot assay endpoints and analyses and clarified endpoint definitions. Section 2.5: Streamlined the study design description to reflect the current design and enrollment. Throughout the SAP: Clarified that since only one participant received sirolimus, no summaries will be provided for the sirolimus cohort. Section 3.1.5: Added LV fractional shortening and LV mass index to the cardiac MRI endpoints. Sections 3.3.1: Added specific immunogenicity endpoints. Sections 3.3.3 and 6.3.5: Clarified endpoint definitions and revised definitions of time to clearance of viral vector shedding endpoints to first identify the first set of 2 consecutive negative results and (2) time to last of 2 consecutive negative results and (2) time to last of 2 consecutive negative results and (2) time to last of 2 consecutive negative results and α=0.05 level, nominal p-values will be presented since no hypothesis testing is to be performed. Sections 5.3.2: Revised to indicate that values below the LLOQ will not be imputed. Sections 5.3.3: Removed sensitivity analysis and revised to impute values below the LLOQ with 0.5*LLOQ.

Sections 5.3.4: Revised to impute values below the
LLOQ or "undetectable" as 0.5*LLOQ for graphical
presentations but not impute for summary statistics. For
values above the ULOQ, missing values will be
imputed as ULOQ for graphical displays and summary
statistics.
Section 5.3.5 and Appendix 2: Revised to include the worst value if multiple values are observed within a
window.
Section 5.3.6 and 6.3.2.2: Moved all analyses to assess
· · · · · · · · · · · · · · · · · · ·
the impact of the COVID-19 pandemic to a supplementary SAP.
Section 6.1.2. Clarified that if there is a local and
central laboratory collection on the same day, the
central laboratory value will be used for analysis. Removed summary of change from baseline to last
observation in laboratory tests. Clarified that
externally normalized values will be normalized to
pediatric textbook ranges. Added content related to
cTn-I analyses.
Section 6.1.3: Added categorical tables for the first 7
days of follow-up and the first 30 days of follow-up.
Section 6.1.4: Removed listing.
Section 6.1.5: Removed summaries of physical exam and neurological exam since any significant findings
are recorded as AEs.
Section 6.3.2.1: Added a sentence to set the total score
to missing if one or more of the 17 items of NSAA is
missing. Clarified the definition of skills gained and
added definitions for rise from floor velocity and 10
meter run/walk velocity.
Section 6.4.2: Added age subgroups
Section 6.5.1: Removed ventilatory support.
Section 6.4.3: Removed reference to flagging specific
mutations in the listing.
Section 8: Moved references to endnotes.
Throughout the SAP: Changed PF-06939926 to
fordadistrogene movaparvovec.
Throughout SAP: Removed refence to sponsor
reporting standards.

2. INTRODUCTION

The investigational product, fordadistrogene movaparvovec (PF-06939926), is a gene therapy viral construct that consists of a recombinant AAV9 vector with a miniaturized version of the DMD gene which encodes the domains minimally required for functionality of the dystrophin protein. Cardiac and skeletal muscle-specific transgene expression is mediated by the synthetic promoter, hCK. This agent is in development for the treatment of DMD, an X-linked neuromuscular disease primarily affecting boys.

Protocol C3391001 is the FIH/FIP study with fordadistrogene movaparvovec. This study aims to evaluate the safety and tolerability following a single dose of fordadistrogene movaparvovec in ambulatory and non-ambulatory participants with DMD. Other objectives include pharmacodynamics of dystrophin expression and distribution, assessments relevant to muscle quality and function and dose selection for future clinical development.

[figure not shown]
This SAP provides the detailed methodology for summary and statistical analyses of the data collected in study C3391001. This document may modify the plans outlined in the protocol; however, any major modifications of the primary endpoint definition or its analysis will also be reflected in a protocol amendment.

2.1. Study Objectives, Endpoints, and Estimands

Objectives	Endpoints	Estimands
Primary Objectives:	Primary Endpoints:	Primary Estimands:
To determine the safety and	Incidence of both	Not applicable
tolerability of a single IV	dose-limiting and	
infusion of fordadistrogene	treatment-related AEs,	
movaparvovec in	inclusive of infusion and	
participants with DMD at	injection site reactions,	
ascending doses.	through 1 year post-treatment.	
	Incidence, severity, and	
	causal relationship of TEAEs	
	through 1 year post-treatment.	
	Incidence and magnitude of	
	abnormal laboratory findings	
	through 1 year post-treatment.	
	Abnormal and clinically	
	relevant changes through	
	1 year post-treatment in:	
	 Physical examination; 	
	Neurological	
	examination;	
	Weight;	
	Vital signs;	
	• ECG;	
	Cardiac MRI- (or	
echocardiogram-)		
	measured LVEF;	
	C-SSRS	

Objectives	Endpoints	Estimands
Secondary Objectives: 1) To determine the amount and distribution of mini-dystrophin expression in the muscle of participants with DMD following a single IV infusion of fordadistrogene movaparvovec at ascending doses.	Secondary Endpoints: Evidence of mini-dystrophin expression and transduction in muscle by immunohistochemistry and LC-MS using muscle biopsies at baseline, 2 or 3 and 6 or 12 months post-treatment	Change from Baseline at early timepoints (2 or 3 months) and later timepoints (12 months; 6-month may be used if 12-month information is not available) in the following measures: • Mini-dystrophin levels, expressed as fmol/mg of total protein, measured by LC-MS assay, LEMPSSLMLEVPTHR (LEMP) peptide • Total dystrophin levels, expressed as fmol/mg of total protein, measured by LC-MS assay, LLQVAVEDR (LLQV) peptide • Total dystrophin levels, expressed as percent normal, measured by LC-MS assay, LLQVAVEDR (LLQV) peptide • Percent of dystrophin and minidystrophin positive muscle fibers derived from the individual fiber MSD data, measured by immunofluorescence assay using DYSB antibody (IF DYSB) • Percent of mini-dystrophin positive muscle fibers derived from the individual fibers MSD data, measured by immunofluorescence assay using mini-dystrophin specific antibody (IF
2) To evaluate long term safety of a single IV infusion of fordadistrogene movaparvovec in participants with DMD at ascending doses.	Incidence, severity and causal relationship of TEAEs and clinically significant safety findings, as described for the primary endpoints (above) through 5 years post-treatment.	mini-dys) Not applicable.

A description of an estimand includes 4 attributes to define the treatment effect of interest. The following subsections provide the details of the estimands linked to the specific objectives and endpoints when applicable.

2.2. Primary Estimand(s)

Not applicable.

2.3. Secondary Estimand(s)

Analyses of the secondary endpoints by population (ambulatory, non-ambulatory, overall) and by dose cohort are described in Section 6.2. For each secondary endpoint, the four attributes associated with the estimand are summarized below.

- Population: Among ambulatory and non-ambulatory participants who meet the inclusion and exclusion criteria, those who receive a single IV infusion of fordadistrogene movaparvovec.
- Variable: Secondary endpoints listed in Section 2.1.

- Intervention effect: Effect of treatment on dystrophin/mini-dystrophin expression and distribution through 1 year post-treatment, regardless of adherence to background and protocol-mandated glucocorticoid regimens.
- Population-level summary: Changes from Baseline (pre- and post-) for treatment difference through 1 year post-treatment

2.5. Study Design

This FIH/FIP study is an open-label, multi-center, ascending dose study designed to evaluate the safety and tolerability of a single IV infusion of fordadistrogene movaparvovec in

participants with DMD. There are 22 participants who received a single dose of fordadistrogene movaparvovec between 1E14 vg/kg and 3E14 vg/kg per the ITR-based method or 2E14 vg/kg per the TG-titer method.

Fordadistrogene movaparvovec at 3E14 vg/kg per the ITR-based titer method is approximately equivalent to 2E14 vg/kg per the TG-titer method. Therefore, participants dosed at 3E14 vg/kg per the ITR-based titer method or at 2E14 vg/kg per the TG-titer method will be grouped in the high dose cohort.

- 1. Ambulatory low dose cohort (N=3): 1E14 vg/kg based on the ITR method
- 2. Ambulatory high dose cohort (N=16): 3E14 vg/kg based on the ITR method or 2E14 vg/kg based on the TG method
- 3. Non-ambulatory high dose cohort (N=3): 2E14 vg/kg based on the TG method
 - Sirolimus non-ambulatory high dose cohort (N=1): 2E14 vg/kg per the TG-based titer method.

Note that a safety profile will be provided for the one participant who received sirolimus. No other summaries will be provided since only one participant received sirolimus.

3. ENDPOINTS AND BASELINE VARIABLES: DEFINITIONS

3.1. Primary Endpoints

- Incidence of both dose-limiting and treatment-related AEs, inclusive of infusion and injection site reactions, through 1 year post-treatment.
- *Incidence, severity, and causal relationship of TEAEs through 1 year posttreatment.*
- Incidence and magnitude of abnormal laboratory findings through 1 year posttreatment.
- Abnormal and clinically relevant changes in physical and neurological examinations, weight, vital signs, ECG, cardiac MRI (or echocardiogram-) measured LVEF, CSSRS through 1 year posttreatment.

3.1.1. Adverse Events

All nonserious AEs and SAEs occurring in a participant during the active collection period, which begins after obtaining informed consent will be recorded on the AE section of the CRF. MedDRA will be used to classify all AEs with respect to SOC and PT.

Relative to fordadistrogene movaparvovec administration:

Any AE that starts following start of treatment of fordadistrogene movaparvovec will be counted as treatment-emergent.

Events that occur in a non-treatment period (applies to screening until study drug administration only) will not be counted as treatment-emergent as this is a single period study.

Relative to sirolimus administration: Any AE that starts following start of treatment of sirolimus will be counted as treatment-emergent.

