6.1. Visit 1 (Screening): Days -196 to -17

This visit will be conducted over a minimum of 2 days to separate the days when the MRI of thigh and upper limb and functional assessments are conducted. Sites may choose to extend this beyond 2 days to accommodate the logistics of completing all testing. It is *highly* recommended that the blood draw for immunogenicity testing be taken at the beginning of the Screening period due to the processing time for these assays.

During Screening, subjects and caregiver(s) will be assessed for study eligibility. All Screening assessments must be completed and reviewed for subject eligibility before the subject is enrolled into the study. Screening tests with results considered by the investigator to be transient and inconsistent with the subject's clinical condition may be repeated once during the Screening period for confirmation of eligibility. Imaging-based examinations for Screening must be reviewed for quality by the central imaging vendor before the subject is enrolled to assure an adequate baseline image has been acquired. If the image is determined to be of poor quality, it may be repeated. The visit window (Day -196 to -17) for screening is to allow for the analysis of laboratory testing, assurance of imaging quality and to provide multiple days to perform the assessments in the order described below. However, certain Screening assessments, namely laboratory tests, functional assessments, thigh and upper limb MRI, would need to be repeated prior to enrollment should the time between these and the planned Baseline visit exceed 12 weeks (84 days), as described in Section 4.2.

If a subject is withdrawn from the study prior to receiving PF-06939926, but wishes to be re-screened and meets the criteria described in Section 4.4, this subject must be re-consented. In addition, all Screening assessments must be repeated with the exception of genetic testing to confirm DMD diagnosis, as well as cardiac imaging, the latter of which would only be repeated if >6 months from when first obtained.

Assessments to be made for the Screening Visit include:

- Informed Consent/Assent: Prior to initiation of any screening assessments the subject (if age of majority, as per Section 12.3) or subject's parent(s) or legal guardian(s) must sign the informed consent document (ICD). If a minor, the subject will be required to provide assent in compliance with local regulations and IRB/EC requirements;

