8.1.4. Time Period for Collecting AE/SAE Information

The time period for actively eliciting and collecting AEs and SAEs ("active collection period") for each subject begins from the time the subject provides informed consent, which is obtained before the subject's participation in the study (ie, before undergoing any study-related procedure and/or receiving investigational product), through and including a minimum of 1 year following administration of the investigational product, also referred to as the Treatment Phase. In the Long-term Follow-up Phase (ie, Years 2 through 5), only SAEs and any AEs believed to be related to the investigational product will be reported.

For subjects who are screen failures, the active collection period ends when screen failure status is determined.

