8.3. Severity Assessment

If required on the AE page of the CRF, the investigator will use the adjectives MILD, MODERATE, or SEVERE to describe the maximum intensity of the AE. For purposes of consistency, these intensity grades are defined as follows:		
MILD	Does not interfere with subject's usual function.	
MODERATE	Interferes to some extent with subject's usual function.	
SEVERE	Interferes significantly with subject's usual function.	

Note the distinction between the severity and the seriousness of an AE. A severe event is not necessarily an SAE. For example, a headache may be severe (interferes significantly with the subject's usual function) but would not be classified as serious unless it met one of the criteria for SAEs, listed above.

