6.1.1. Adverse Events

Incidence and severity of TEAEs will be reported.

Deaths and SAEs will be listed. The following will be summarized by dose cohort and ambulatory status at baseline:

- Incidence and severity of TEAEs (all causalities and treatment-related)
- Withdrawals due to TEAEs; and
- Incidence of SAEs (all causalities and treatment-related).

To evaluate the safety of sirolimus:

The incidence and severity of TEAEs (all causalities and treatment-related) relative to the initiation of treatment with sirolimus through 30 days post-last dose of sirolimus (approximately 44 days post-fordadistrogene movaparvovec infusion per sirolimus administration schedule) will be summarized for those participants who received sirolimus (sirolimus cohort) versus those who did not (non-sirolimus cohort).

No summaries will be provided by sirolimus cohort status since only one participant received sirolimus.

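### SAP 3.1.1 defines treatment-emergent AEs by start date alone, so an AE already open at infusion that then worsens may be left out of the primary TEAE tables

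*SAP*

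**What the plan says.** - **The rule.** SAP 3.1.1 classes an AE by when it began: "Any AE that starts following start of treatment of fordadistrogene movaparvovec will be counted as treatment-emergent". Events between screening and study drug administration "will not be counted as treatment-emergent as this is a single period study". A parallel definition for sirolimus also uses the start of the event only. Neither document has a clause for an AE that increases in severity.
- **Where the flag is used.** SAP 3.1 names as a primary endpoint "Incidence, severity, and causal relationship of TEAEs through 1 year posttreatment". SAP 6.1.1 tabulates the incidence and severity of TEAEs, all-causality and treatment-related, and withdrawals due to TEAEs. SAP 6.2.3 carries the same analyses to 5 years. SAP 6.1.1 lists SAE incidence separately and does not tie it to TEAEs.
- **When collection starts.** Under Protocol 8.1.4 the collection period "begins from the time the subject provides informed consent". Protocol Section 6 schedules "Visit 1 (Screening): Days -196 to -17".
- **How severity is recorded.** Protocol 8.3 says that, where the AE page of the CRF asks for it, the investigator picks one of three grades "to describe the maximum intensity of the AE".

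**The concern.** The first question in a safety study is what happened, or got worse, after infusion. The Protocol asks it: Schedule of Activities footnote b has sites look at Days 4, 7 and 10 for AEs that are new or have worsened. Protocol 8.1.5 treats an AE as related if the product caused it or contributed to it, so a pre-dose AE aggravated by the vector can be judged related. The SAP rule counts only the new ones.

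The pre-dose period is also not empty. It can include meningococcal vaccination (Protocol 5.7.1) and a muscle biopsy under anaesthesia at Baseline (Protocol 6.2), so an AE opened then and still open on Day 1 is a realistic case.

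At stake is a primary endpoint in cohorts of 3 and 16, where one participant visibly changes a percentage. Any error goes one way, towards a cleaner profile.

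**Working it through.** **Step 1. Plan's own figures.** The plan states no TEAE rate, and Protocol 9.1 rests the sample size on clinical considerations, so there is no rate to reproduce. The SAP 2.5 cohort sizes are ambulatory low dose 3, ambulatory high dose 16 and non-ambulatory high dose 3. The sum 3 + 16 + 3 = 22 agrees with the stated total.

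**Step 2. Apply the rule to each way an event can be recorded.**

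| Situation | Start date on the record | TEAE under SAP 3.1.1? |
|---|---|---|
| AE first appears after infusion | Post-dose | Yes |
| AE open at infusion, worsens, new record opened | Post-dose | Yes |
| AE open at infusion, worsens, same record continued | Pre-dose | No |
| Condition in medical history progresses after dosing and is entered as an AE | Post-dose | Yes |

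Only the third row is lost.

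**Step 3. Do the documents say whether the second or third row applies?** Protocol 8.1.1 (CRF recording details), 8.1.4.2 (recording on the CRF) and 8.3 (severity) do not require a new record when severity rises, and do not forbid one. One maximum intensity per AE is compatible with a single record carried across Day 1, but does not prescribe it.

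**Step 4. Which outputs use the flag?**
- Affected: TEAE incidence and severity (all-causality and related), withdrawals due to TEAEs, and the 5-year versions of these.
- Not dependent on it: SAE listings and incidence (SAP 6.1.1); laboratory abnormalities, tabulated also for abnormal baseline (SAP 6.1.2); vital signs, ECG, cardiac imaging and weight, summarised as changes (SAP 6.1.3, 6.1.4, 6.1.6, 6.1.7).
- Partly exposed: examination changes, which SAP 6.1.5 reports through the AE tables. Protocol 9.2 does have post-dose examination findings that meet the AE definition captured as AEs.

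**Step 5. Direction.** AEs that start post-dose are a subset of AEs that start or worsen post-dose. Adding the worsening clause can therefore raise TEAE incidence or leave it unchanged. It can also move a participant to a higher severity category. It cannot lower incidence.

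**Step 6. Size.** For k participants newly counted under one preferred term in a group of n, the shift is 100 × k/n points.

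| n | k = 1 | k = 2 | k = 3 |
|---|---|---|---|
| 3 | 33.3 | 66.7 | 100.0 |
| 16 | 6.25 | 12.5 | 18.75 |
| 22 | 4.5 | 9.1 | 13.6 |

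k is not in the documents; 0 to 3 is an assumed range, and at k = 0 the shift is 0.

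**The case against.** The strongest reply is that no loss has been shown. Four things must coincide: an AE opens after consent, is still open at infusion, then worsens, and stays in one record. The last depends on the CRF and its completion guidance, which are not among the documents. This stands, and it rules out several stronger readings.

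- **That TEAE incidence is understated.** The documents support only that it may be.
- **That every pre-existing problem that worsens is missed.** Protocol 8.2.1 lists worsening of the underlying disease as an AE in itself. Conditions present at entry can sit in medical history (SAP 3.4). Progression entered as an AE after dosing has a post-dose start and is counted.
- **That the maximum-intensity convention shows worsening stays in the old record.** Protocol 8.3 is conditional on the CRF asking for severity, and says only how to grade an AE.
- **That the whole safety profile is affected.** Several primary safety summaries do not use the flag (step 4). An AE that became serious after dosing still reaches the SAE tables. The first primary endpoint, dose-limiting and treatment-related AEs, is not worded in terms of TEAEs, although the related-AE tables specified in SAP 6.1.1 are for TEAEs and SAEs.
- **That 33.3 or 6.25 points is a bias estimate.** Each is 1/n for one preferred term. It applies only if the participant has no other qualifying event under that term. Incidence of any TEAE does not move if the participant has any other TEAE.

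What the reply does not remove is the rule itself. It rests on onset only, it expressly shuts out pre-dose events, and no text in either document rescues an AE kept in one record.

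**Conclusion.** The point holds as a gap in the definition, not as a demonstrated undercount. An AE opened between consent and Day 1 that becomes more severe after infusion, under one record with its pre-dose start date, is left out of the TEAE incidence, severity and treatment-related tables. For such events these primary summaries may be understated and cannot be overstated. The gap is mainly non-serious AEs.

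The amount cannot be calculated from the documents. It is zero if no such AE exists, if worsening was entered as a new AE, or if the participant already counts for that term. Otherwise each participant newly counted adds 33.3 points in a cohort of 3, 6.25 in the cohort of 16, or 4.5 of 22 overall, for that term.

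The sirolimus definition has the same fault but little consequence, since SAP 2.5 has one participant on sirolimus and plans a safety profile rather than summaries.

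**What to change.** 1. In both definitions in SAP 3.1.1 (fordadistrogene movaparvovec and sirolimus), define a TEAE as an AE that starts, or increases in severity, after the start of treatment. State that the exclusion of pre-dose events does not apply to one that later increases in severity.
2. New wording alone will not identify past cases. SAP 2.5 shows all 22 participants already dosed, and the CRF may hold only one maximum intensity per AE, which would not date a rise. So list every AE ongoing at infusion, ask sites whether and when its severity rose after dosing, and record any such rise with its own onset date.
3. Put the same question for every AE on that list, whatever its suspected cause, because the answers will be given retrospectively in an open-label study.

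**Cost.** A short SAP edit, a listing, and what should be a small number of site queries among 22 participants. The downside is reliance on retrospective judgement, and possibly a few more events counted. If the list is empty or no severity rose, the tables stand unchanged and the report can say so.
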